## NUMBER OF PLATELET TRANSFUSIONS

The incidence of platelet transfusions will be monitored by the investigator (or appropriately delegated study site personnel) from randomization. The number of transfusions administered (if used), along with date and start/stop times, will be specified and recorded in the CRF. In order to minimize missing data for the primary endpoint, “Not Done” (or “Not Applicable”) will be collected on the CRF to indicate subjects who did not receive a platelet transfusion.

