## ANY RESCUE PROCEDURE FOR BLEEDING

Any rescue procedure for bleeding will be monitored by the investigator (or appropriately delegated study site personnel) from randomization onwards. Any rescue procedure for bleeding, including number of transfusions administered (if used), along with start and end dates/times, will be recorded. In order to minimize missing data for the primary endpoint, “Not Done” (or “Not Applicable”) will be collected on the CRF to indicate subjects who did not receive rescue therapy.

The following are considered as rescue procedures when used specifically for bleeding:

- Platelet transfusion
- FFP
- Cryoprecipitate
- Vitamin K (phytonadione)
- Desmopressin
- Recombinant activated factor VII
- Aminocaproic acid
- Tranexamic acid (added per Amendment 01)
- Whole blood transfusion
- Packed red cell transfusion
- Surgical intervention or interventional radiology

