5.2 STUDY SUBJECTS

5.2.1 Definitions of Analysis Sets

Full Analysis Set (FAS): The FAS is the group of all subjects who are randomized into the study.

Per Protocol Analysis Set (PP): The PP is the group of all randomized subjects who receive protocol-assigned study drug and do not meet any of the following criteria:

- Baseline platelet count of $>50 \times 10^9/L$
- Subjects who were enrolled in the study despite not being planned for transfusion even in the event of no significant increase of platelet count
- Taking prohibited prior medications or prior transfusion
- Presence of significant bleeding at baseline
- Did not have a protocol permitted procedure on Day 8 - 15
- Received dose different from the intended dose
- Received $<80\%$ of the total dose or received $>40\%$ of total dose without food
- No elective procedures or elective procedure outside day 8-15
- Subject received platelet transfusion before knowing V4 platelet count
- Subject refused platelet transfusion

Subjects who met any of the criteria listed above will be excluded from the PP due to possible introduction of bias.

Safety Analysis Set: The Safety Analysis Set is the group of subjects who receive at least one dose of study drug and have at least one post dose safety assessment.

The number (percentage) of subjects in each analysis set will be summarized by treatment groups using descriptive statistics. The summaries for FAS and PP will be based on subjects “as randomized”. The summary for Safety Analysis Set will be based on subjects “as treated”.

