5.3.5 Handling of Missing Data, Drop-outs, and Outliers

Unless stated otherwise, missing values will be considered as non-responders in responder analyses for all efficacy analyses; observed data will be used in other type of efficacy analyses. Details can be found in [Sections 5.4, Efficacy Analyses](#).

All safety analyses will be performed based on the observed data only.

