5.4.1 Primary Efficacy Analyses

The primary efficacy variable is the proportion of subjects who do not require a platelet transfusion or any rescue procedure for bleeding after randomization and up to 7 days following an elective procedure.

The null hypothesis is that the proportion of subjects not requiring a platelet transfusion or any rescue procedure for bleeding after randomization and up to 7 days following an elective procedure is the same between the avatrombopag and placebo treatment groups. The corresponding alternative hypothesis is that the proportion of subjects not requiring a platelet transfusion or any rescue procedure for bleeding after randomization and up to 7 days following an elective procedure is not the same between avatrombopag and placebo. This hypothesis will be tested separately with each baseline platelet count cohort.

The proportion of subjects not requiring a platelet transfusion or any rescue procedure for bleeding will be tested between the individual avatrombopag treatment group (40 or 60mg) and matching placebo within each baseline platelet count cohort ($<40 \times 10^9/L$ or from 40 to $<50 \times 10^9/L$), each at a significance level of $\alpha=0.05$ using the generalized Cochran Mantel Haenszel (CMH) test adjusting for the risk of bleeding associated with the elective procedure (low, moderate, or high based on Amendment 02 categorization).

- For subjects with platelet count $<40 \times 10^9/L$ at baseline, the treatment comparison will be carried out between the 60 mg avatrombopag treatment group (Group A) versus matching placebo (Group B).
- For subjects with platelet count from 40 to $<50 \times 10^9/L$ at baseline, the treatment comparison will be carried out between the 40 mg avatrombopag treatment group (Group C) versus matching placebo (Group D).

This study will be considered as positive if statistical significance is achieved for primary efficacy endpoints for both baseline platelet count cohorts.

The 95% CI for the proportion of subjects not requiring a platelet transfusion or any rescue procedure for bleeding will be calculated for each treatment group within each baseline platelet count cohort. In addition, the 95% CI for the difference between avatrombopag and matching placebo will also be provided within each baseline platelet count cohort using normal approximation method.

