Since the HCC status is included in the randomization stratification for safety purposes only, not for efficacy consideration, HCC will not be included in the CMH model for the primary efficacy analysis.

Subjects with missing information about the primary efficacy outcome due to early withdrawal or other reasons will be considered as having received a transfusion for the primary analysis.

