8.2 MISSING DATA HANDLING

For the responder analysis of primary and secondary efficacy endpoints, subjects without the required platelet transfusion data or platelet count data will be considered as non-responders. For other efficacy analyses, unless specified otherwise, observed data will be used without missing data imputation. Details can be found in [Sections 5.4](#), Efficacy Analyses.

Safety data will be analyzed using observed data with no imputation for missing values.

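### Does the SAP leave the primary endpoint undefined for an untransfused subject who never has the elective procedure?

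*SAP*

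**What the plan says.** SAP 5.4.1 defines the primary outcome as needing neither a platelet transfusion nor a rescue procedure for bleeding "after randomization and up to 7 days following an elective procedure". The analysis set is everyone randomised: "The FAS is the group of all subjects who are randomized into the study" (SAP 5.2.1).

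Three SAP statements deal with incomplete outcomes:

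- 5.4.1, on the primary analysis: "Subjects with missing information about the primary efficacy outcome due to early withdrawal or other reasons will be considered as having received a transfusion".
- 5.3.5: unless stated otherwise, "missing values will be considered as non-responders in responder analyses for all efficacy analyses".
- 8.2: for the primary and secondary responder analyses, "subjects without the required platelet transfusion data or platelet count data will be considered as non-responders".

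The SAP knows that some subjects will have no procedure. The per-protocol exclusions in 5.2.1 include "No elective procedures or elective procedure outside day 8-15", and 8.1 gives such subjects substitute visit windows, for by-visit summaries only.

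In Protocol 9.5.1.3, a not-done or not-applicable entry "will be collected on the CRF to indicate subjects who did not receive a platelet transfusion", and the same kind of entry "will be collected on the CRF to indicate subjects who did not receive rescue therapy". Protocol 9.3.3 lets a subject who stops study drug have the procedure outside the study. SAP 9 places derivation rules in separate documents, which are not among those reviewed.

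**The concern.** The end of the outcome window is tied to an event that some randomised subjects will not have. Take a subject who attends visits, receives no transfusion and whose procedure is cancelled. Two scorings can be argued:

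- **Success.** Transfusion and rescue are both recorded as not given. Nothing is blank, so the missing-data rule is not triggered.
- **Failure.** The seven days after the procedure never happened, so the outcome is unknown and the missing-data rule applies.

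Subjects are enrolled because the investigator expects the procedure to call for a transfusion (inclusion criterion 3). A cancelled procedure removes that reason, so success scoring would credit the cancellation as efficacy, in either arm. A procedure outside the study raises a related worry: Table 5 schedules the transfusion and rescue assessments only at Visits 2 to 5, so the last entry could precede the procedure.

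At stake is the count of primary responders. One reclassified subject moves a cohort's rate by 1/33 = 3.0 points on placebo or 1/67 = 1.5 points on avatrombopag, and the trial is positive only if both cohorts succeed. The listed sensitivity analyses do not isolate the effect. The observed-case and modified-endpoint analyses depend on the same notion of missing, and the per-protocol set drops these subjects together with those meeting eight other criteria.

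**Working it through.** **1. Which reading the text supports.** The quantity to be known is status through seven days after a procedure. A not-done entry shows that no transfusion had been given by the time of the entry. It cannot show what happened in an interval that did not occur. The 5.4.1 rule is not limited to withdrawals, since it extends to other reasons, and 8.2 asks whether the required data are present. Both lead to failure, the SAP's default throughout.

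**2. Procedure outside the study.** The endpoint refers to an elective procedure without requiring that it be done in the study. If status is known for seven days afterwards, it can be scored as observed; if not, it is missing and fails. Table 5's transfusion row is not the only source:

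- Protocol 9.5.1.3 monitors transfusion and rescue from randomization.
- 9.4.7 records any therapy given during the study.
- 9.5.1.6 collects transfused platelet units at scheduled and unscheduled visits, and Table 5 includes resource use and bleeding at Visit 6.
- 9.5.7 has the site ask at each visit about care by another physician.
- 9.3.3 requires Visit 6 after early discontinuation.

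**3. Reproducing the planned power.** Inputs from SAP 4: 67 and 33 per cohort, 53% versus 18%, Fisher's exact test, two-sided 0.05. Enumerating all 68 × 34 outcomes gives 92.6% per cohort, consistent with the stated figure above 90%. For both cohorts, if independent, 0.926² = 85.8%.

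**4. Size of the difference between the scorings.** Let q be the share of an arm that is followed, untransfused and without a procedure in the study, and r the response rate among the rest. The scored rate is

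- success scoring: q + (1 − q)r
- failure scoring: (1 − q)r

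The two treatment differences therefore differ by exactly q₁ − q₀ (1 = avatrombopag, 0 = placebo). Example, q = 2% on avatrombopag only: success gives 0.02 + 0.98 × 0.53 − 0.18 = 35.9 points; failure gives 0.98 × 0.53 − 0.18 = 33.9 points.

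Every q below is an assumption. Power is per cohort by Fisher's exact test.

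| q, avatrombopag / placebo | Difference, success / failure (points) | Power, success / failure |
|---|---|---|
| 2% / 2% | 34.3 / 34.3 | 90.7% / 91.9% |
| 5% / 5% | 33.25 / 33.25 | 87.7% / 90.8% |
| 2% / 0% | 35.9 / 33.9 | 93.8% / 91.2% |
| 0% / 2% | 33.4 / 35.4 | 89.2% / 93.3% |
| 3% / 10% | 28.2 / 35.2 | 72.8% / 93.9% |
| 10% / 3% | 37.2 / 30.2 | 94.3% / 85.0% |

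In the first four rows the scorings differ by 1.2, 3.1, 2.6 and 4.1 points. The last two show what a seven-point imbalance would do. For scale, 5% is about 3 of 67 and 2 of 33 subjects.

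The direction is not fixed. With 5% / 5% but response rates of 70% and 40%, success scoring has the higher power (75.2% against 73.1%).

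**5. Rejection rate with no drug effect (18% in both arms).** CMH figures come from 1,000,000 simulated cohorts per setting, with an assumed 60/15/25 low/moderate/high risk split and equal response across risk strata.

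| q, avatrombopag / placebo | Fisher, success / failure | CMH, success / failure |
|---|---|---|
| 5% / 5% | 3.7% / 3.7% | 4.9% / 4.8% |
| 2% / 0% | 3.9% / 3.8% | 4.9% / 4.9% |
| 5% / 0% | 5.4% / 4.0% | 6.6% / 5.2% |
| 10% / 0% | 11.4% / 4.4% | 13.3% / 5.9% |

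Marked inflation needs both the success reading and a strong imbalance.

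**6. One illustration near the design rates.** Reclassifying 3 of 67 (4.5%) and 4 of 33 (12.1%) changes 37/67 versus 9/33 (p = 0.011, success scoring) to 34/67 versus 5/33 (p = 0.0009, failure scoring). Both are significant.

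**The case for a change.** The best case for a change is that a primary-outcome scoring rule belongs in the SAP before unblinding, that two programmers could read the present text differently, and that one sentence would settle it. If failure is what is meant, writing it costs nothing. At 5% in both arms, success scoring takes power below 90%, and the sample-size section states no allowance for such subjects.

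Part of this stands. The text is not explicit, the success reading cannot be excluded on wording alone, and with widely different shares in the two arms the choice would matter.

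It does not make the plan defective. The sentence asked for would restate the result that the existing missing-data rule already gives on its ordinary reading. Double-blind treatment gives no evident reason for cancellations to differ by arm, although a delay for high platelet counts is permitted and could fall unevenly; a delayed procedure is still a procedure, and its window still opens. Scoring administrative cancellations as failures is itself a choice with a cost, so an added rule would not be a pure gain. The detail may also already sit in the separate derivation documents.

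**Conclusion.** No change to the plan follows. The SAP does not name the followed, untransfused subject without a procedure, but its missing-outcome rule, its general default and its data-handling section together lead an analyst to score that subject as a non-responder. Whether a procedure outside the study leaves the outcome known or missing can be decided from the several other places where transfusions and care are recorded.

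Under the planned rates, the two readings differ by about 1 to 4 points of power per cohort when assumed shares are equal at 2% or 5%, or are 2% in one arm and none in the other. Under no effect, the equal 5% and the 2% / 0% cases show no inflation of the rejection rate. The stated power is correct.

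This rests on the shares being small and similar between arms. The documents neither give them nor suggest that they differ, and a gap such as 3% against 10% would move the estimated difference by 7 points. It also rests on analysts taking the ordinary reading; the derivation documents could not be checked.

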5.4.1.1 Sensitivity Analysis

The following analyses will be considered as sensitivity analyses:

- PP analysis: The same primary efficacy analyses described in [Section 5.4.1](#) will be repeated based on the PP analysis set.
- Observed case: The same primary efficacy analyses described in [Section 5.4.1](#) will be repeated based on observed data. Subjects with missing information about the primary efficacy outcome will be excluded from this analysis.
- Fisher's exact Test: The same primary efficacy analyses described in [Section 5.4.1](#) will be carried out using Fisher's exact test.
- Modified primary efficacy endpoint: Proportion of subjects who do not require a platelet transfusion after randomization and up to 7 days following an elective procedure. This efficacy endpoint will be analyzed using the same approach as primary efficacy analysis using FAS

Additional sensitivity analyses may also be explored, if deemed appropriate.

5.4.1.2 Subgroup Analysis

The primary efficacy variable described in [Section 5.4.1](#) will be summarized by each subgroup listed below.

- age group (<65 and ≥65 years old)
- sex (male and female)
- race (white, black, Asian and other)
- geographic region
- bleeding risk associated with the elective procedure (low, moderate and high based on Amendment 02 categorization)
- MELD score (<10, 10-14, and >14)
- CTP grade (A, B, and C)
- Disease etiology (alcoholic liver disease, chronic viral disease, nonalcoholic steatohepatitis, other)

Additional subgroups may also be explored, if deemed appropriate.

5.4.2 Secondary Efficacy Analyses

There are 2 secondary efficacy endpoints in this study:

- Proportion of responders, defined as subjects who achieve target platelet counts of $\geq 50 \times 10^9/L$ on Procedure Day (prior to receiving a platelet transfusion or undergoing the elective procedure)
- Change from baseline in platelet count on Procedure Day (prior to receiving a platelet transfusion or undergoing the elective procedure)

The analysis of the secondary efficacy variables, as defined above, will proceed following a sequential gatekeeping testing procedure to control the family-wise Type I error rate at a significance level of $\alpha=0.05$.

5.4.2.1 Proportion of subjects achieved platelet counts of $\geq 50 \times 10^9/L$ on the Procedure Day

The proportion of subjects who achieve platelet counts of $\geq 50 \times 10^9/L$ on the Procedure Day will be analyzed first.

The proportion of subjects with platelet counts of $\geq 50 \times 10^9/L$ on the Procedure Day will be tested between the individual avatrombopag treatment group (40 or 60mg) and matching placebo separately within each baseline platelet count cohort ($< 40 \times 10^9/L$ or from 40 to $< 50 \times 10^9/L$), each at a significance level of $\alpha=0.05$ using the generalized CMH test adjusting for the risk of bleeding associated with the elective procedure (low, moderate, or high based on Amendment 02 categorization).

The 95% CI for the proportion of subjects with platelet counts of $\geq 50 \times 10^9/L$ on the Procedure Day will be calculated for each treatment group within each baseline platelet count cohort. In addition, the 95% CI for the difference between avatrombopag and placebo will also be provided within each baseline platelet count cohort using normal approximation method.

Subjects with missing platelet count on Procedure Day will be considered as not achieving the platelet count of $\geq 50 \times 10^9/L$ for this analysis.

5.4.2.2 Change from baseline in platelet count on the Procedure Day

The second secondary efficacy variable, change from baseline in platelet count on the Procedure Day, will be analyzed only if the first secondary efficacy variable is statistically significant for both baseline platelet count cohorts.

The change from baseline in platelet count on Procedure Day will be analyzed using the Wilcoxon rank sum test separately within each baseline platelet count cohort ($< 40 \times 10^9/L$ or from 40 to $< 50 \times 10^9/L$), each at a significance level of $\alpha=0.05$. The treatment difference

between avatrombopag and placebo will be provided within each baseline platelet count cohort using Hodges-Lehmann estimation along with associated asymptotic (Moses) 95% CIs.

Last observation carried forward will be used for subjects with missing platelet count on Procedure Day for this analysis.

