Study E5501-G000-202 evaluated the efficacy, safety, and population PK of once-daily oral avatrombopag dosing, in subjects with chronic liver diseases and thrombocytopenia prior to elective surgical or diagnostic procedures. The primary efficacy endpoint was the proportion of responders with platelet count increases from baseline of  $\geq 20 \times 10^9/L$  and a platelet count of  $\geq 50 \times 10^9/L$  once from Day 4 through Day 8. The proportion of responders for all avatrombopag-treated subjects was 48.4% compared with 8.1% in the combined placebo group ( $P < 0.0001$ ). All doses of avatrombopag achieved a significantly higher proportion of responders compared with their respective cohort placebo arms and the highest platelet count responses were observed between Days 10 to 14 after first dose. In addition, avatrombopag appeared well tolerated in this patient population. There was no clear trend regarding the incidences of AEs between placebo and avatrombopag treatment groups, and the commonly reported treatment-emergent adverse events (TEAEs) and serious TEAEs were consistent with the disease state of the patient population. The findings from Study E5501-G000-202 suggest that avatrombopag would be an effective therapy for the treatment of thrombocytopenia in patients with chronic liver disease, prior to an elective procedure.

For more detailed information regarding effects in humans, please refer to the Investigator Brochure.

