**Table 4 Clinical Laboratory Tests**

Category	Parameters
Hematology	
Complete Blood Count	hematocrit, hemoglobin, platelets, RBC count, and WBC count with differential (basophils, eosinophils, lymphocytes, monocytes, total neutrophils [segmented and bands])
Coagulation panel	prothrombin time, activated partial thromboplastin time, international normalized ratio
Chemistry	
Electrolytes	bicarbonate, chloride, potassium, sodium
Liver function tests	alanine aminotransferase, alkaline phosphatase, aspartate aminotransferase, direct bilirubin, total bilirubin, gamma-glutamyl transpeptidase
Renal function parameters	blood urea nitrogen, creatinine
Other	albumin, calcium, cholesterol, creatine phosphokinase with fractionation, globulin, glucose, lactate dehydrogenase, phosphorus, total protein, triglycerides, uric acid
Urinalysis	bacteria, casts, crystals, epithelial cells, glucose, ketones, occult blood, pH, protein, RBCs, specific gravity, WBCs
Protocol specified	
Females only	serum beta-human chorionic gonadotropin pregnancy tests, urine pregnancy tests
Platelet function tests a	eg, p-selectin and integrin IIbβ3 with and without an agonist. The following agonists will be used: 0.5 μM ADP, 20 μM ADP, 1.5 μM TRAP, or 20 μM TRAP (eg, platelet aggregation with an agonist. ADP will be used as the agonist) (revised per Amendment 02)

ADP = adenosine diphosphate, RBC = red blood cell, TRAP = thrombin receptor agonist peptide, WBC = white blood cell

a: Performed only at selected sites

Clinical laboratory tests during the study will be performed by the designated central laboratory. All blood and urine samples will be collected and sent to the central laboratory on the day of collection unless otherwise instructed. When a hematology test is required, 2 blood samples will be collected: 1 for central laboratory analysis and 1 for local laboratory analysis. Investigators will utilize the platelet count result received from the local laboratory hematology test analysis to qualify subject's entry into the study, and also for clinical assessments.

Only platelet count data from local laboratories, including the date and clock time of collection of the sample, will be collected and entered into the CRF for analysis. All other hematological parameters will be collected and loaded into the database for analysis according to results derived from the designated central laboratory.

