**Table 5 Schedule of Procedures/Assessments in Study E5501-G000-310**

Phase Period Visit	Prerandomization	Randomization			Follow-Up	
	Screening	Baseline	Treatment	Procedure Day	5	6 c
Day	1	2	3	4 a, b	5	6 c
Day	Days -14 to -1	Day 1	Day 4 (±1 day)	Day 10 (+3 days)	7 Days Postprocedure (+3 days)	Day 35 (+3 days)
Procedures/Assessments						
Subject informed consent	X					
Inclusion/Exclusion criteria	X	X				
Demographics	X					
Medical history	X					
CTP and MELD Scores	X					
BCLC grade d	X					
Prior/concomitant medications	X	X	X	X	X	X
Health care resource use		X	X	X	X	X
Adverse events	X	X	X	X	X	X
Physical examination e	X			X	X	X
Vital signs (including height, weight)	X f	X		X	X	X
ECG (12-lead)	X	X	X			X
Hematology (including platelet count by local laboratory) g	X h	X h	X	X	X	X
Coagulation	X			X		X
Serum chemistry, liver function tests, CPK with fractionation, urinalysis i	X			X		X

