8 DEFINITIONS AND CONVENTIONS FOR DATA HANDLING

8.1 VISIT WINDOW

Study Day 1 is defined as the date of the first dose of study drug. The analysis visits defined below will be used in the by-visit summaries:

Visit	Target Visit Date	Visit Window	Analysis Visit
Visit 2 (Baseline)	Study Day 1	Less or equal to Study Day 1	Last visit on or before Study Day 1
Visit 3	Study Day 4	Study Day 2 to 7	Closest visit to Study Day 4
Visit 4	Study Day	Subjects with procedure:	Subjects with platelet

Visit	Target Visit Date	Visit Window	Analysis Visit
(Procedure Day)	10 to 13	Study Day 8 to actual procedure day Subjects without procedure: Study Day 8 to 13	transfusion: last visit before transfusion Subjects with procedure but without transfusion: last visit before procedure Subjects without platelet transfusion or procedure: closest visit to Study Day 10
Visit 5	7 Days post procedure	Subjects with procedure: 1 to 10 days post actual procedure day Subjects without procedure: Study Day 14 to 20	Subjects with procedure: visit closest to 7 days post actual procedure day Subjects without procedure: closest visit to Study Day 17
Visit 6	Study Day 35	Subjects with procedure: Greater or equal to actual procedure day +11 days Subject without procedure: Greater or equal to Study Day 21	Closest visit to Study Day 35

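### The Procedure-Day platelet-change test ignores the bleeding-risk strata, and its LOCF-based estimate has no planned alternative (low impact)

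*SAP*

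**What the plan says.** **Test and estimate.** SAP 5.4.2.2 compares arms by a Wilcoxon rank sum test within each cohort and reports a Hodges-Lehmann difference with a Moses interval. Protocol 9.7.1.6 names the same test. Bleeding risk is a randomisation stratum (protocol 9.4.3, SAP 3.2) and enters both CMH tests (SAP 5.4.1, 5.4.2.1). SAP 5.3.2 lists only those two endpoints for adjustment.

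**Missing counts.** SAP 5.4.2.2 states: "Last observation carried forward will be used for subjects with missing platelet count on Procedure Day for this analysis". The protocol gives no missing-data rule for this endpoint.

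**Windows.** In SAP 8.1, Visit 3 takes "Study Day 2 to 7". Visit 4 takes "Study Day 8 to actual procedure day", or Days 8 to 13 if there is no procedure.

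**Timing of effect.** Protocol 7.1.2.3 reports from Phase 2 that "the highest platelet count responses were observed between Days 10 to 14 after first dose".

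**Other analysis of the same variable.** SAP 5.4.3.1 plans an exploratory Wilcoxon test by visit on observed data, without a Hodges-Lehmann estimate.

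**The concern.** There are two separate matters.

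First, this is the only gated efficacy test that leaves out a stratum used in randomisation. Stratified allocation balances the arms within risk levels. If those levels differ in platelet change, an unstratified test counts the between-level spread as noise, so it rejects too rarely under the null and loses power.

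Second, a subject with no count in the Visit 4 window contributes an earlier one. The endpoint is meant to describe Procedure Day, and the carried value usually predates most of the drug's effect. At stake is a modest understatement of the reported difference on the last gated endpoint, with no second Hodges-Lehmann estimate to show how much the rule matters.

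**Working it through.** **1. The plan's own figure.** The documents give no power for platelet change. For the primary endpoint they claim more than 90% per cohort with 67 vs 33 subjects and 18% vs 18 + 35 = 53%. Exact Fisher power by full enumeration is 92.6%, so the claim holds. I use it only to set an effect scale: Φ⁻¹(0.53) − Φ⁻¹(0.18) = 0.99 SD. Applying this to platelet change is an assumption.

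**2. What LOCF carries.** Visit 4 opens on Day 8 and Visit 3 closes on Day 7. With no Visit 4 value, the carried count is from Day 7 or earlier, or is the baseline count, giving a change at or near zero. This is inferred from SAP 8.1; 5.4.2.2 does not say it. Which of the two applies is unclear. Protocol Table 5 schedules "Hematology (including platelet count by local laboratory" at Visit 3, and the text under Table 4 says "When a hematology test is required, 2 blood samples will be collected: 1 for central laboratory analysis and 1 for local laboratory analysis". The platelet-count schedules in the synopsis, 9.5.1.3 and 9.5.1.4 omit Visit 3.

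**3. Strata.** For stratum k with n treated, m placebo and N = n + m, let W be the treated rank sum.
- Wilcoxon (no strata): z = [W − n(N+1)/2] / √[nm(N+1)/12].
- Van Elteren: z = Σ w_k[W_k − n_k(N_k+1)/2] / √Σ w_k² n_k m_k(N_k+1)/12, with w_k = 1/(N_k+1).

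Simulated cohorts had 100 subjects, 2:1 blocks of 3 and 10,000 runs per setting. Assumed: risk shares 60/20/20, 25% with HCC, normal errors, no missing data.

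| Shift per risk level | Type I error: Wilcoxon / van Elteren | Power at 0.6 SD | Power at 0.99 SD |
|---|---|---|---|
| 0 | 4.9% / 5.0% | 77.7% / 76.8% | 99.3% / 99.3% |
| 0.5 SD | 3.7% / 5.3% | 74.2% / 78.1% | 99.2% / 99.4% |
| 1 SD | 1.3% / 5.1% | 58.1% / 77.1% | 97.1% / 99.4% |

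A second set (shares 60/25/15, 6,000 runs) gave type I error of 5.1/3.9/1.6% against 5.0/5.1/5.2%. A third gave 5.0/3.9/1.5% for Wilcoxon and about 5% for van Elteren. The largest gain at 0.99 SD is 99.4 − 97.1 = 2.3 points. The cost without prognostic strata, at 0.6 SD, is 77.7 − 76.8 = 0.9 point.

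Van Elteren on LOCF data with 20% missing (equal in both arms, or 20% vs 5%) rejected 4.8–6.1% under the null in 6,000-run settings. Repeating the two highest with 20,000 runs gave 5.0% and 5.3%, so the excess is mostly simulation noise.

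**4. LOCF dilution.** The documents give no missing share, no SD and no early effect, so all are assumed. With true shift 0.99 SD, equal random missingness and no strata effect, the Hodges-Lehmann estimates are (LOCF / full data):

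| Missing | Baseline carried | Day-4 value with 25% of the effect carried |
|---|---|---|
| 5% | 0.936 / 0.996 = −6.0% | 0.942 / 0.986 = −4.5% |
| 10% | 0.865 / 0.990 = −12.6% | 0.899 / 0.984 = −8.6% |
| 20% | 0.723 / 0.976 = −25.9% | 0.820 / 0.991 = −17.3% |

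A second set used platelet units: change 30 (SD 25) vs 3 (SD 12), with treated early means from 0 to 19. The high early means allow for Phase 2, where 48.4% of treated subjects met a response criterion "once from Day 4 through Day 8". Doses and criterion differed there. With missingness in the treated arm or both arms, the estimate fell 0.8–2.5% at 2% missing, 1.7–6.5% at 5% and 3.4–13.4% at 10%. On a shift of 30 − 3 = 27, the 5% case is about 0.5–1.8 ×10⁹/L. Placebo-only missingness raised the estimate by 0.5–0.6% at 5% and 1.1–1.2% at 10%.

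**5. Alternatives when treated low responders are missing more often.**

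| Missing | LOCF | Observed data | Multiple imputation |
|---|---|---|---|
| 5% | −0.5 to −3.2% | +3.2 to +3.4% | +2.4 to +2.6% |
| 10% | −0.9 to −7.0% | +6.5 to +6.8% | +4.9 to +5.2% |

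Imputation does not help the test. At 0.6 SD, 0.5 SD per level and 10% missing, van Elteren power is 72.8% with LOCF and 72.7% with imputation.

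**The case against.** The strongest reply is that nothing here is an error. The Wilcoxon test is valid and is the one the protocol names. The bias mostly runs against the drug, and no later confirmatory test depends on this endpoint. No passage says that procedure risk predicts platelet change. With the platelet-unit inputs (about 1.25 pooled SD), the planned analysis has at least 99.9% power even at 20% missing, strata not modelled. Missing values are also limited: Visit 4 accepts counts from Day 8, and Table 5 note b asks for Visit 4 assessments at early withdrawal.

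Most of this stands, and it sets the size of the point. Two parts do not remove it. A withdrawal count taken before Day 8 still falls in the Visit 3 window. The observed-data analysis in 5.4.3.1 has no Hodges-Lehmann estimate.

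A reader might infer three stronger points that the documents do not support:
- **LOCF contradicts the SAP's general rule.** It does not. SAP 5.3.5 opens its rule with an exception clause ("Unless stated otherwise, missing values will be considered as non-responders in responder analyses for all efficacy analyses"), and 8.2 allows stated exceptions to observed data.
- **The unstratified test endangers type I error.** It errs towards too few rejections. With LOCF and unequal missingness (20% vs 5%, either way) it rejected 4.3–5.3% under the null.
- **Multiple imputation should replace LOCF as the main analysis.** It leaves power unchanged and overstates the effect by about 5% at 10% missing if low responders drop out, where LOCF stays conservative. It also relies on a Visit 3 local count that the protocol schedules in one place and omits in others.

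**Conclusion.** The point holds as a low-impact improvement.

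**Strata.** The test omits a randomisation stratum that the two preceding gated tests use. It is valid. It is conservative only if bleeding risk is prognostic for platelet change: type I error about 3.9% and 1.5% at assumed shifts of 0.5 and 1 SD per level. At 0.99 SD the power gain is at most about 2 points. Larger gains appear only at smaller effects, such as the 0.6 SD used above, which no document gives.

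**LOCF.** It usually dilutes the Hodges-Lehmann estimate, by about 2–7% at 5% missing, and no alternative estimate is planned. The direction is not fixed: placebo-only missingness raises the estimate slightly, and LOCF could overstate the effect if treated subjects whose counts later fell were the ones missing.

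The sizes rest on assumed missing shares, early effects, SDs, stratum shares and stratum shifts. Neither the primary conclusion nor type I error control is at risk.

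**What to change.** Before unblinding:

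1. **SAP 5.4.2.2 and 5.3.2.** Use the van Elteren test stratified by bleeding risk (Amendment 02 categories). Report a matching Hodges-Lehmann estimate, the shift at which the van Elteren statistic is zero, with a 95% CI formed from the shifts that this test does not reject. Record in SAP Section 7 the departure from protocol 9.7.1.6; protocol 9.7.5 already requires a study-report note.
2. **Keep LOCF as the main rule.** State which count is carried, including whether it must precede any transfusion, and reconcile the protocol passages on a Visit 3 local count.
3. **Sensitivity analyses.** Prespecify a Hodges-Lehmann estimate and CI on the observed Procedure-Day data already analysed in 5.4.3.1 and, optionally, a multiple-imputation estimate. State that both can overstate the effect if low responders are missing. Report missing counts by arm.

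Cost: SAP wording, modest programming, and under about 1 point of power at 0.6 SD if the strata are not prognostic. Coverage of the stratified interval was not simulated and should be checked, because the high-risk stratum may be small.
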